Primary Hypothesis: Three doses of DNase-tPA, when compared to three doses of tPA via chest drain will reduce the time to discharge after chest drain insertion in children hospitalized with pleural empyema.

Secondary Research Questions: Will there be differences between the groups with respect to other outcomes related to efficacy, cost and safety? The following outcomes will be assessed:

- a) Time to meeting discharge criteria.
- b) Time to drain removal.

Version June 29, 2017.

- c) Duration of fever, defined as the number of days with temperature >38°C.
- d) Need for ventilator support or non-invasive ventilation following intervention.
- e) Risk of serious bleed, defined as intrapleural bleeding resulting in a drop in hemoglobin of greater than 20 g/L or needing a transfusion.
- f) Need for further interventions, defined as the need for further intervention such as placement of another chest drain (by any technique) or surgical intervention such as thoracotomy and decortication, video-assisted thoroscopic surgery, or pneumonectomy.
- g) Hospital readmission related to pleural empyema or its treatment within three months of discharge.
- h) Cost of the hospitalization.
- i) Mortality.
- j) Amount of effusion present at the time of drain removal (exploratory outcome).

Secondary Hypotheses: DNase-tPA, when compared to tPA via chest drain, will:

- a) Reduce the time of fever, time to meeting discharge criteria, time to drain removal and cost.
- b) Not result in an increase in need for ventilator support or non-invasive ventilation following intervention, nor an increase in risk of serious bleed, nor any need for further intervention, nor the risk of hospital readmission, nor the risk of mortality.

TRIAL DESIGN (see Appendix 1 for trial schematic)

Design: The study design will be a superiority randomized controlled trial in a parallel group, 1:1, two arm design.

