Interventions: Patients will be randomized to receive either: (a) tPA [alteplase (Cathflo®), Roche] at a dose of 4 mg followed by a placebo (saline) administered intrapleural via chest drain once daily for 3 doses; or, (b) tPA at a dose of 4 mg followed by DNase [dornase alfa (Pulmozyme®), Roche] at a dose of 5 mg. Weight-based dosing will not be used for tPA or DNase, as pleural concentrations are unpredictable and variable. Pediatric studies of tPA^{29 31} and guidelines²¹ have utilized adult dosing. DNase will be constituted by the research pharmacies in clear liquids in a polyethylene syringe⁴². Since the stability of a tPA-DNase admixture is unknown, the drugs will be administered sequentially with a 1 hour indwelling time for each drug as described in the aforementioned adult trial. For tPA, the contents of the vial will be diluted to a total volume of 10 ml normal saline (tPA) for children less than or equal to 10 kg and 20 ml for children > 10 kg. A flush of 5 ml of normal saline will be instilled after drug administration. Following the instillation of tPA the drain will be clamped for one hour and then will be opened to drain under suction at a pressure of -20 cm H₂O for one hour. Then, either DNase or placebo will be instilled as a volume to 10 ml with normal saline for children less than or equal to 10 kg and 20 ml for children > 10 kg, followed by the same 5 ml normal saline flush, the same one hour period of clamping and the same one hour period of drainage at -20 cm H₂O. Thus in total, each cycle of tPA-study drug instillation and drainage will take 4 hours to complete. The pharmacies will prepare the two arms (DNase or placebo) in a manner such that both are identical (packaging, colour, volume, texture, and odour) to ensure blinding. The contents of the vials (tPA followed by DNase or placebo) will be instilled into the chest drain by clinicians caring for the child. The first dose of tPA will be given immediately (within 1 hour) after insertion of the chest drain by the interventional radiologist or surgeon in the procedure suite or by clinicians on the ward and DNase or placebo will be instilled on the ward. On the following day (day 1) and the subsequent day (day 2) a dose of tPA followed by the study drug will be administered in the morning, between 9 and 10 am, in a similar fashion. Thus, each patient will receive a total of three doses of either tPA or tPA-DNase over 48 hours.

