Clinical Samples at the Hospital for Sick Children: At the SickKids site only, consent will be obtained to store samples of chest tube drainage from subjects. These samples will be used for future testing to determine the microbiological cause of empyema.

Concomitant Medication: Patients in either arm will not receive any intrapleural drug other than directed from this study.

Criteria for discontinuing study interventions: Patients who develop anaphylaxis or serious bleeding (requiring a blood transfusion or resulting in a hemoglobin drop of ≥ 20 g/L) while receiving study interventions will not receive further study drugs. Patients whose chest drains is displaced will only be replaced if clinically indicated for pleural fluid drainage and not for study drug administration alone. Outcomes for all patients who do not received the full study interventions will be analyzed in the group they were assigned to.

Standard care: In keeping with a pragmatic-type trial design, all children will receive standard care for this condition including supportive care, laboratory investigations, imaging, antibiotics, chest drain care and removal and discharge as outlined in the standard care guidelines. Although some variability is expected in care among treating physicians, rigorous randomization and blinding should ensure that confounders are equally distributed between groups. A detailed care map will be adapted from the existing clinical practice guideline co-authored by team investigators (EC and SM) together with the Canadian Pediatric Society. Specific elements in the care plan include:

- a) *Antimicrobial management* - Patients in both treatment arms will receive standard therapy for pleural empyema in children as directed by the responsible physician and standardized guidelines. All participating hospitals currently recommend a 2nd or 3rd generation cephalosporin (cefuroxime or ceftriaxone or cefotaxime) as the empiric antimicrobial therapy with possible addition of clindamycin or vancomycin if *S. Aureus* is a suspected etiology. It is expected that antibiotic regimens will be tailored in line with local microbiology advice.
- b) *Drain insertion* - Chest drains will be placed using an image guided percutaneous technique by interventional radiologists or by a surgeon using a standardized technique under anesthesia agreed upon by all sites. The recommended size of catheter drain used will be an 8 or 10 French pigtail catheter.

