- a. *Time to meeting discharge criteria:* This is defined as the time, measured in hours, and reported in days rounded to a single decimal point, from insertion of the chest drain to meeting discharge criteria. This will be assessed by a research assistant on a twice daily basis (9 AM and 4 PM) and defined as: no fever (temperature less than 38°C) for 24 hours, normal respiratory rate for age [using the World Health Organization (WHO) age-specific criteria (< 50 breaths/min for 2-12 months, < 40 breaths/min

for 1 to 5 years, and < 20 breaths/min for ≥ 5 years)], no hypoxia (transcutaneous oxygen saturations in room air less than 92%), and drinking fluids well.

b. *Time to drain removal*: This is defined as the time, measured in hours, and reported in days rounded to a single decimal point, from drain insertion to drain removal.

c. *Duration of fever after intervention*: This is defined as the duration, measured in hours, and reported in days rounded to a single decimal point, of fever (defined as temperature $>38^{\circ}\text{C}$ taken by any method) from insertion of the chest drain until resolution. This will be recorded by a research assistant daily.

d. *Need for ventilatory support or non-invasive ventilation following the intervention*.

e. *Serious bleeding*: This is defined as intrapleural bleeding resulting in a drop in hemoglobin of greater than 20 g/L or needing a transfusion.

f. *Need for further interventions*: This is defined as the need for further intervention such as placement of another chest drain (by any technique) or surgical intervention such as thoracotomy and decortication, video-assisted thoroscopic surgery, or pneumonectomy.

g. *Hospital readmission*: Any hospital readmission after discharge from hospital for initial treatment for pleural empyema within three months related to pleural empyema or its treatment (e.g. harm). All hospital readmissions will be categorized as empyema-related or not.

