Sample size: The primary endpoint is time to hospital discharge after intervention. The mean time to hospital discharge after chest tube insertion and fibrinolytics varies. Published studies with treatment arms that have included chest drain with fibrinolytics as the primary mode of insertion reported hospital days after the intervention from 6 to 15 days.^{23,24} Hospital length of stay tends to be shorter in published RCTs compared with observational studies of empyema, and the most recently published RCT using an identical tPA dosing regimen to that which we are proposing described a mean (SD) stay of 6.8 (2.9) days.³¹ The desired power for the current proposal is 90% to detect a difference of 2 days in the mean time to hospital discharge between the treatment arms. Based on discussions with clinical experts in the field, hospital administrators and parents of children with pleural empyema, it is believed that a 2 day difference between treatment groups is a minimal clinically meaningful difference, and this has been used in previous empyema trials.²⁷ The adult DNase trial found about a 50% difference in length of stay between treatment and placebo groups.⁴²

Sample size was thus calculated assuming a type 1 error rate of 0.05 (2 sided), power (1-β) of 90%, a standard deviation of 2.9 days for each group to detect a difference of 2 days to be 46 per group. Calculations were performed based on a t test of independent groups. While we do not anticipate any post-randomization ineligibility, for example from misdiagnosis, we will increase the sample size by 5% to account for this possibility (total of 49 patients per group). There will be no other adjustment to the sample size requirements due to loss to follow-up for the primary outcome as the primary outcome is assessed in hospital where the research coordinator will be able to ensure complete data collection.

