Secondary outcomes and exploratory outcome: For the secondary and exploratory outcomes that are continuous variables (e.g. duration of drain insertion, hospital stay after intervention to meeting discharge criteria, duration of fever after the intervention, amount of hemithorax occupied by pleural effusion in radiographs) the difference between the two means with the 95% confidence intervals will be presented. The student's t test will be used to detect a difference between the treatment groups. Dichotomous outcomes (serious bleeding, need for further interventions, need for ventilatory support, mortality) will be described as the absolute number and proportion. A Fisher's exact test will be used to detect a significant ($p < 0.05$) difference between the two treatment arms. The treatment effect will also be presented as the relative risk with 95% confidence intervals. These analyses will be viewed as hypothesis generating, and therefore, no correction for multiple testing is planned.

Data Monitoring and Safety: Data monitoring will be conducted with a Data Monitoring Committee (DMC) composed of a pediatric hospitalist, a respiratory physician and an interventional radiologist. The DMC will be completely independent of the investigators, and will be provided with clinical information from the trial case report forms for death, surgical events and adverse events, including those that were described in the adult DNase trial (hemoptysis, gastrointestinal bleeding, chest pain, nausea, transient confusion and rash). The DMC will be able to request additional information from clinicians.

Adverse Event Reporting: All serious unexpected adverse events will be reported to the REB; as per SickKids REB guidelines. All serious adverse drug reactions to the study medication will be reported to Health Canada within 15 calendar days or for death or life-threatening events, within 7 calendar days. In the latter case, a follow-up report will be filed within 8 calendar days. Adverse reactions will be managed according to the standard clinical management practices. All adverse events and adverse reactions will also be reported to the PI within 24 hours.

[figure not shown]
Quality Assurance: This project will be monitored by The Applied Health Research Centre (AHRC) during the data collection phase of the project. The aim is to ensure that all researchers are maintaining

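### Do the two meanings of serious bleeding, one for the outcome and one for stopping study drug, call for a change to the plan?

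*Combined protocol and SAP*

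**What the plan says.** The Secondary Research Questions (item e) list "Risk of serious bleed, defined as intrapleural bleeding resulting in a drop in hemoglobin of greater than 20 g/L or needing a transfusion". Item e of the secondary outcomes in the Methods repeats the same definition: "intrapleural bleeding resulting in a drop in hemoglobin of greater than 20 g/L or needing a transfusion". Both name the pleural site and set the hemoglobin limit strictly above 20 g/L, with transfusion as the alternative.

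Under Criteria for discontinuing study interventions, further study drug is withheld after anaphylaxis or "serious bleeding (requiring a blood transfusion or resulting in a hemoglobin drop of ≥ 20 g/L) while receiving study interventions". The label is the same, but no site is given and the limit includes 20 g/L itself. This rule operates only during dosing, in which "each patient will receive a total of three doses of either tPA or tPA-DNase over 48 hours".

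The outcome feeds a secondary hypothesis that adding DNase will not bring "nor an increase in risk of serious bleed". The analysis is simple: "Dichotomous outcomes (serious bleeding, need for further interventions, need for ventilatory support, mortality) will be described as the absolute number and proportion", followed by Fisher's exact test and a relative risk. The plan calls these analyses hypothesis generating. Under Data Monitoring and Safety, the committee receives case report form information on adverse events, "including those that were described in the adult DNase trial (hemoptysis, gastrointestinal bleeding, chest pain, nausea, transient confusion and rash".

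**The concern.** One term stands for two sets of events, and the protocol neither reconciles them nor says that they differ on purpose. A child could bleed, be taken off study drug for serious bleeding, and then be recorded as not having had serious bleeding. In the report, the number stopped for serious bleeding might exceed the number in the outcome row of that name.

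The matter looks worth raising because events will be few. The background section gives a 2% local prevalence of bleeding with any fall in hemoglobin, so one child moved in or out could be a large part of the row that addresses the bleeding hypothesis. The outcome wording also leaves some doubt whether the intrapleural restriction applies to the transfusion limb. At stake is the description of harm. The comparison of time to discharge does not depend on it.

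**Working it through.** **Step 1: the two definitions side by side**

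| | Secondary outcome e | Stopping criterion |
|---|---|---|
| Site | intrapleural | not named |
| Hemoglobin drop | more than 20 g/L | 20 g/L or more |
| Transfusion | counts | counts |
| Period | none stated | while study interventions are being given |

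**Step 2: where they can disagree.** Cross site (intrapleural, extrapleural), drop (below, exactly, above 20 g/L) and transfusion (no, yes): 2 × 3 × 2 = 12 types of bleed. Each definition has two possible readings. The stopping criterion may mean any site, or it may loosely restate the intrapleural term already defined in the Secondary Research Questions. In the outcome, the intrapleural restriction may cover both limbs (the natural reading) or only the hemoglobin limb.

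- Stopping criterion, any site: 5 types per site (two untransfused, at or above 20 g/L; three transfused), 2 × 5 = 10. Intrapleural only: 5.
- Outcome, restriction on both limbs: 1 untransfused type above 20 g/L + 3 transfused = 4. If any transfusion counts: 4 + 3 extrapleural transfused = 7.

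| Stopping criterion | Outcome | Stopped, not counted | Counted, not stopped |
|---|---|---|---|
| any site (10) | both limbs intrapleural (4) | 6 | 0 |
| any site (10) | any transfusion (7) | 3 | 0 |
| intrapleural (5) | both limbs intrapleural (4) | 1 | 0 |
| intrapleural (5) | any transfusion (7) | 1 | 3 |

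Between 1 and 6 types can therefore be stopped without being counted. The one type common to all four rows is an intrapleural bleed with a drop of exactly 20 g/L and no transfusion. These are cells of a grid, not frequencies. The documents give no rate for any of them.

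**Step 3: does timing add to this?** No. The stopping period lies inside any plausible period for the outcome, so a bleed that stops drug also falls where the outcome would count it. Timing can produce only the reverse: a bleed after the last dose that is an outcome event with no drug left to stop. That is expected.

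**Step 4: size.** Inputs: 49 per arm (Sample size section) and the 2% local prevalence (Fibrinolytics section, any hemoglobin drop). Because that 2% uses a looser criterion than either definition, it serves only as a rough guide.

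- Expected bleeds per arm: 49 × 0.02 = 0.98. In the trial: 98 × 0.02 = 1.96.
- Chance of at least one in the trial: 1 − 0.98^98 = 0.86.
- One child in an arm: 1/49 = 2.0%. The exact (Clopper-Pearson) 95% interval moves from 0 to 7.3% at 0/49 to 0.1 to 10.9% at 1/49.
- Fisher's exact two-sided p, 49 per arm: 1 v 0, 1.00; 2 v 0, 0.49; 5 v 0, 0.056; 6 v 0, 0.027.

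With no events in the other arm, one reclassified child crosses 0.05 only in going from 5 to 6. At 2%, the binomial probability of 5 or more events in a given arm of 49 is 0.003.

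**Step 5: are the excluded bleeds lost?** No. Hemoptysis and gastrointestinal bleeding are named among the adverse events that go to the Data Monitoring Committee. Children who stop early stay in their assigned group, so stopping for bleeding removes nobody from the analysis.

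**The case for a change.** The strongest case for a change rests on site. The protocol's summary of the adult trial lists five serious bleeding events: two intrapleural, two gastrointestinal and one hemoptysis. Three of the five were thus outside the pleura. If a comparable bleed here had a hemoglobin drop of, say, 25 g/L without transfusion, and the stopping criterion means any site, the child would be stopped for serious bleeding and left out of the outcome however its wording is parsed. With about one bleed expected per arm, that child could be much of the evidence. New wording would be cheap, and so would a descriptive count by arm of bleeding at any site.

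Part of this stands. The label is shared, the difference is unexplained, and the mismatch can occur. The rest is weaker. Both gastrointestinal bleeds were in the DNase-only arm, which this trial does not have. That leaves one hemoptysis under a regimen used here, with no hemoglobin drop reported. The site gap also depends on reading an unnamed site as any site; only the difference at exactly 20 g/L is unconditional. An any-site row is something an analyst may reasonably add to the safety table from adverse event data, but the outcome is not wrong without it. The wording does not by itself show that the case report form records hemoglobin drop for extrapleural bleeds, so such a row might be less complete.

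**Conclusion.** The mismatch is real and is one of labelling. No change to the plan follows. A stopping criterion and an outcome serve different purposes and need not cover the same events. An outcome confined to the pleural space fits the protocol's account of fibrinolytic harm, which names intrapleural bleeding as the exception to an otherwise clean record. Both definitions can be followed as written. An analyst applies item e to the outcome row, lists discontinuations by the stopping criterion, and adds a footnote that the two differ. That resolves any apparent discrepancy in the report.

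The size is small: normally no child, plausibly one, which is 2.0 percentage points of an arm of 49 with p = 1.00 for 1 v 0. Sample size and the primary comparison are untouched, and the affected test is one that the plan itself calls hypothesis generating. This rests on the 2% figure as a rough guide to frequency and on adverse event reporting working as described.

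The secondary outcome definition and the discontinuation section do read differently on site and on the limit at 20 g/L. Reconciling that wording is a matter for the investigators, and nothing here favours one threshold, site or stopping rule over another.

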Therefore, although there is a biological rationale and clinical efficacy data from adults, currently it is not known whether the addition of DNase to tPA will provide improvement in outcomes for pediatric pleural empyema.

SUMMARY OF THE EVIDENCE TO DATE FOR PEDIATRIC PLEURAL EMPYEMA

Pleural empyema is a rising problem in children and leads to significant short-term morbidity. Rigorous evidence with pediatric data is essential to inform clinical decision-making. The proposed trial brings clinical experts with a strong track record in outcomes research in pediatric empyema together with methodological experts in clinical trials in an effort to improve the outcomes of children admitted to hospital with pleural empyema.

Although there is still some ongoing controversy, the best evidence from randomized controlled trials seems to suggest that either VATS or small bore percutaneous chest tube placement with instillation of fibrinolytics result in the best outcomes in pediatric pleural empyema as measured by hospital length of stay, although chest tube with fibrinolytic therapy may be more cost-effective. Fibrinolytics are a safe and effective therapy based on observational and randomized control trial evidence. However, persistent short-term morbidity associated with prolonged hospitalization and pain/discomfort from chest tubes, as well as the need for secondary salvage surgical procedures. Based on a well-designed study in adults, there may be an additional benefit from the addition of intrapleural DNase to tPA, but this requires study in a pediatric population as the underlying disease (e.g. microbiology and natural history), and other, age-related biological factors may potentially affect response to treatment. This randomized controlled trial is designed to address the efficacy, cost effectiveness and safety of DNase combined with tPA compared with tPA alone in the management of childhood pleural empyema.

STUDY AIMS

Over-arching aim: The overarching aim of this research collaborative is to improve outcomes for children with pleural empyema.

Primary Research Question: In previously well children who present with pleural empyema, does intrapleural DNase with tissue plasminogen activator (tPA) via chest drain for three doses over 48 hours improve the time to hospital discharge compared with three doses over 48 hours of tPA alone ?

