h. *Cost of the hospitalization*: An economic evaluation will compare the relative costs of DNase-tPA with tPA alone in previously well children who present with pleural empyema, using patient-level data from the trial. We will conduct the analysis from a hospital's perspective because hospital administrators will be making reimbursement decisions for this intervention. Since empyema is an acute condition and the long-term consequences are negligible, the time horizon of the analysis will be the length of hospital stay. Since the primary effectiveness outcome is length of hospital stay or time to hospital discharge, which can be expressed in monetary terms (i.e. hospitalization cost), we will only compare the costs of the two strategies to avoid double-counting the effectiveness. The cost of each patient includes the cost of intervention (DNase-tPA or tPA alone) and costs incurred during the hospital stay ("hospitalization cost"). We will obtain the hospitalization costs of each patient from case costing data from hospital financial departments. We will calculate mean cost per patient by intervention group, based on initial intervention assignment, and incremental cost using simple linear regression:

$$C_i = \alpha_i + \beta t_i + \varepsilon_i$$

Where C_i is the cost for each patient i , α is the intercept term, t is an intervention dummy term ($t=1$ if the patient received DNase-tPA and $t=0$ for tPA alone), and ε is the stochastic error term. The regression coefficient β estimates the incremental cost of DNase-tPA compared with tPA alone. The regression statistics will show mean cost per patient by intervention group and the uncertainty around the mean estimates. We will also conduct sensitivity analysis to assess the robustness of the results.

i. *Mortality*: this will include mortality from any cause during the hospitalization for empyema.

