Blinding: Patients, their parents or other caregivers, site investigators, research assistants and coordinators, treating physicians (pediatricians, radiologists, and interventional radiologists or surgeons), treating nurses, and data managers will be blinded to the treatment allocation. Group allocation will be concealed until the final data analysis is performed. Intervention drugs will be blinded by the research pharmacy. Both arms will be constituted by the research pharmacies in clear liquids in a polyethylene container⁴² in a manner such that both are identical (packaging, colour, volume, texture, and odour) to ensure blinding. After obtaining the treatment number from the central randomization centre, the study pharmacist will retrieve the corresponding vial and one of its treatment number labels will be attached to the patient's case report form (CRF).

Unblinding Procedures: We do not anticipate any circumstances that would require unblinding as knowledge of study arm is not anticipated to affect any treatments for patients.

Data collection methods: Data collection for outcome measures will be mainly collected in hospital by the Research Assistant (RA). At baseline, the following data will be obtained: age, sex, duration of antibiotic treatment prior to chest drainage insertion (days), duration of fever prior to chest drain insertion (days), hypoxia in room air (oxygen saturations less than 92% in room air prior to intervention), microbiologic identification of causative agent (blood culture results, throat swab, pleural fluid culture, pleural fluid PCR), ultrasound of chest: pleural effusion size >10 mm <10 mm, stage of empyema on ultrasound of chest: Stage 1: anechoic nonseptated fluid; Stage 2: echoic fluid without septation; and Stage 3: septated fluid and Stage 4: septations with solid appearing components comprising more than one third of the effusion.⁵³ All ultrasounds will be reviewed by a blinded study radiologist (BC). In addition, patients will receive a follow-up phone call from the RA at 3 months enquiring about any possible readmissions and ongoing symptoms of fever, shortness of breath and/or exercise intolerance.

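### Index-stay cost is a valid declared outcome, but the promised sensitivity analysis should name one result that adds empyema-related readmissions to three months (low priority)

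*Combined protocol and SAP*

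**What the plan says.** Item h of the secondary outcomes (Cost of the hospitalization) takes the hospital's perspective because "hospital administrators will be making reimbursement decisions for this intervention". It states that "the time horizon of the analysis will be the length of hospital stay", on the grounds that empyema is acute and its lasting effects are too small to matter. Each child's cost is the intervention plus the hospital stay, taken from the hospitals' case-cost records. The item closes with "We will also conduct sensitivity analysis to assess the robustness of the results", without saying what will be varied.

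Item g (Hospital readmission) covers "Any hospital readmission after discharge from hospital for initial treatment for pleural empyema within three months related to pleural empyema or its treatment", and adds that "All hospital readmissions will be categorized as empyema-related or not". Under Data collection methods, "patients will receive a follow-up phone call from the RA at 3 months enquiring about any possible readmissions". The Secondary Hypotheses expect DNase-tPA to reduce cost and not to increase various risks, "nor the risk of hospital readmission" among them. The evidence summary in the background is broader: "This randomized controlled trial is designed to address the efficacy, cost effectiveness and safety of DNase combined with tPA compared with tPA alone".

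Item h also says that mean costs are grouped by the arm first assigned, but its regression sets t to 1 for a child who received DNase-tPA. The section on discontinuing study interventions analyses children who do not get the full intervention in their assigned group.

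**The concern.** The reason given for the horizon speaks to long-term effects. A readmission in the first three months is not a long-term effect, and item h neither mentions it nor says why its cost is left out. Yet a related readmission to a study centre is a cost to that hospital, which is the perspective chosen. The hypothesised saving would come largely through earlier discharge, and readmission is the natural place to look for an offset or a further gain.

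An administrator reading the cost result would therefore see the index stay in money and the readmissions only as a count. A rough conversion would be possible, but not one based on the trial's own case costs. What is at stake is how completely the reimbursement question is answered, not the primary result.

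**Working it through.** **1. Is readmission cost covered anywhere?** Setting the sections side by side:
- Item h: cost ends at index discharge; sensitivity analysis promised, content open.
- Item g and Data collection methods: related readmissions to three months identified and classified.
- Statistical Analysis, Primary outcome: children lost to three-month follow-up are reported but left out of those analyses.

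No section adds readmission cost or explains its omission. Item h's argument against double-counting does not supply the reason: the effectiveness outcome also stops at index discharge, so readmission cost is not counted in it.

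**2. What does the horizon leave out?** Let p be the related readmission risk and c the mean cost per readmission (D = DNase-tPA, T = tPA alone).

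Omitted incremental cost per child = p_D × c_D − p_T × c_T

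This is zero when rates and costs are equal, positive if readmission costs more under DNase-tPA and negative if it costs less. The documents give neither p nor c.

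**3. Scale, under assumptions.** In bed-days, with a common length L, the omitted amount is d × L, where d is the risk difference. Assumed: d of 2, 5 or 10 points in either direction; L of 3 days (assumed) or 6.8 days. The 6.8 is the mean stay for initial drainage quoted under Sample size, used only as a stand-in. The share is of the 2-day target difference.

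| d | L = 3 days | Share of 2 days | L = 6.8 days | Share of 2 days |
|---|---|---|---|---|
| ±0.02 | ±0.06 | 3% | ±0.136 | 6.8% |
| ±0.05 | ±0.15 | 7.5% | ±0.34 | 17% |
| ±0.10 | ±0.30 | 15% | ±0.68 | 34% |

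One extra readmission in an arm of 49 is 3/49 = 0.06 or 6.8/49 = 0.14 bed-days per child.

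**4. Against the trial's precision.** The plan's group size reproduces: SD 2.9, difference 2, two-sided 0.05 and 90% power give 45.17 by the exact t calculation, hence 46; 46 × 1.05 = 48.3, hence 49. With 49 per arm:
- SE of the stay difference = 2.9 × √(2/49) = 0.586 days
- 95% half-width = 1.985 × 0.586 = 1.16 days (t on 96 df)
- 0.06/1.163 = 5% and 0.68/1.163 = 58%, so every scenario lies inside the half-width.

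This is the precision of length of stay. The documents give no SD for cost.

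**5. Few events.** Even 5 of 49 against 0 of 49 gives a two-sided Fisher p of 2 × C(49,5)/C(98,5) = 2 × 0.0281 = 0.056.

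**6. Follow-up.** In the investigators' earlier and more demanding cohort (Feasibility and Timelines), 6 of 88 were lost at one month and 8 more at six months: 6/88 = 7% and 14/88 = 16%. Applied to 49 per arm, that is about 3 to 8 children. This is a guide, not a forecast, since here the contact is one short call.

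**7. Definition of t.** A child assigned DNase-tPA who stops after the first tPA instillation, before any DNase, counts as DNase-tPA by assignment but t = 0 by receipt. The two rules agree for every child who was given the assigned study drug at least once.

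**The case against.** The strongest reply is that index-stay cost is exactly what was declared. Item h of the Secondary Research Questions asks for the cost of the hospitalization, the outcome carries the same name, and cost-effectiveness appears only in summary text. This stands: the base case answers the question it names and should stay.

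Readmission is also a separate secondary outcome, no increase is expected, and secondary analyses are treated as hypothesis-generating. All true, and the reason for low priority. But a count is not a case cost, and an expectation under test does not remove the value of checking it.

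The scenarios above are assumptions without support in the documents. That also stands; they show scale only.

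Finally, adding three-month data brings incomplete observation into a measure that is otherwise complete. Counting unreached families as zero cost would depart from the plan's rule of omitting children lost to follow-up, and would bias readmission cost downward. This shapes the fix: zero-counting should appear only as a second, labelled assumption.

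A reader might infer that the cost comparison is wrong, or tilted towards DNase-tPA. The documents support neither. Nothing in them suggests more readmissions with DNase-tPA, and if there were fewer, the index horizon would understate its saving.

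**Conclusion.** A cheap improvement of low priority, not an error in the base case. The stated reason for the horizon does not reach three-month readmissions, which the trial already records and which, at study centres, fall within the chosen perspective. The effect on incremental cost could go either way, is nil under equal rates and costs, and cannot be sized from the documents. The 0.06 to 0.68 bed-days per child rests wholly on assumed risk differences and readmission lengths. The primary conclusion does not depend on it.

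The definition of t is a small but real inconsistency within item h, and also with the rule of analysing children as assigned. It would change coding only for a child who received no study drug or the wrong one.

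**What to change.** - Keep index-stay cost as the base case.
- Within the sensitivity analysis already promised, name one result: index-stay cost plus case-costed, empyema-related readmissions to study centres within three months, by assigned arm.
- Present it for children with three-month follow-up, in line with the plan's rule on loss to follow-up. Show a version that counts unreached families as zero, unless study-centre records show a cost, only as a second, labelled assumption.
- Report by arm the number not reached and the number readmitted elsewhere, whose costs stay unknown.
- Define t = 1 as assigned to DNase-tPA.

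Cost: a few sentences in the analysis plan, a short wording change for t, and a small finance-data request, with a check that consent covers later cost records (the consent pages were not available for this review). Downsides: three-month follow-up may be incomplete and readmissions will be few, so the result will be imprecise and should be described as such.
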